11.2 STATISTICAL ANALYSIS

All data will be analyzed by the CCLR at the University of Waterloo. Summary statistics will be produced (e.g. mean, standard deviation). Data analysis will be conducted using Statistica and / or SPSS. Descriptive statistics will be provided on information regarding baseline variables (age, gender, refractive error distribution, etc.). Analysis of variables will be conducted separately on each eye, and data will not be pooled. A Binomial test will be used to analyze the results for the count data of subjective preferences. The number of “no preference” will be evenly distributed to the two options on the basis they would be equally likely to choose either.

Table 5 lists the primary outcome variables and anticipated statistical procedures.

Table 5: Outcome variables and anticipated statistical procedures

Variable	Analysis	Statistical test
Analogue scales/Numeric scales/Preference scales/VA Lens parameters, Biomicroscopy (continuous variables)	Effect of lens type	RMANOVA/MANOVA/ Friedman /Wilcoxon matched pairs test Tukey HSD post hocs Paired t-test Chi-square test
Biomicroscopy (ordinal variables)	Effect of lens type	Friedman Wilcoxon matched pairs test
Analogue scales/Numeric scales/Lens parameters, Biomicroscopy (continuous)	Relationship between slit lamp findings and analogue scales	Pearson correlation - r
Biomicroscopy (ordinal variables)	Relationship between slit lamp findings and analogue scales	Spearman correlation - rho

The critical alpha level for statistical significance will be set at $p \leq 0.05$, with no adjustments for multiple comparisons.

All participants who were evaluated will be used in the analysis. In the event of missing data, individual data points will be excluded in the analysis and not extrapolated from the collected data.

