2 OBJECTIVES

The objective of the study is to evaluate the performance of MyDay toric test lens when worn on a daily disposable wear modality over 1 week.

The primary outcome variables are:

- Comfort and lens preference with respect to comfort (subjective ratings)
- Dryness and lens preference with respect to dryness (subjective ratings)
- Visual quality and lens preference with respect to visual quality (subjective ratings)

[REDACTED]

[REDACTED]

[REDACTED]

[REDACTED]

[REDACTED]

[REDACTED]

[REDACTED]

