4 MATERIALS AND METHODS

4.1 STUDY DESIGN

4.1.1 OVERALL DESIGN

This study is a prospective, double-masked (investigator and participant), bilateral, randomized, cross-over dispensing study comparing the MD-T test lens against the 1-DAM-T and DACP-T control lenses. Each participant will be randomized to wear either the test or one of the controls with similar/comparable lens parameters optimized for vision. Both test and control lenses will be

used in their approved daily disposable lens wear modality for one (1) week. It is anticipated that this study will involve up to 4 scheduled visits:

Visit 1: Baseline includes screening and dispense of lens pair #1,

Visit 2: 1-week follow-up visit of lens pair #1 and dispense of lens pair #2,

Visit 3: 1-week follow-up visit of lens pair #2 and dispense of lens pair #3,

Visit 4: 1-week follow-up visit of lens pair #3 and study exit.

The study design is shown in Figure 1.

[figure not shown]

Figure 1: Study Design

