4.8.3 DISPENSING LENS PAIR #1

The participant will be assigned a randomization ID and the first pair (lens pair #1) of contact lenses (either test or one of the control lenses) will be selected according to the randomization table.

- Lens pair #1 will be provided to participants in a manner which does not unmask the participant, as described in Section 4.7.4.
- The lenses will be inserted by the participant.
- The contact lenses will be allowed to settle for 10 minutes.
- The participant will be asked to give subjective binocular ratings for:
 - Comfort at insertion (0-10 scale)
 - Ease of insertion (0-10 scale)
 - Speed of settling (0-10 scale)
 - Visual quality (0-10 scale)
 - Vision stability (0-10 scale)
 - Overall satisfaction (0-10 scale)
- Monocular and binocular logMAR visual acuity will be recorded with high contrast letters under high (300-600 lux) and low (1-5 lux) room illumination.
- Lens surface and fit will then be assessed and graded according to the CVI grading scales for the following:
 - Lens wettability (0-4 scale)
 - Centration (mm)
 - Post-blink movement (mm)
 - Toric mark visibility

- Lens orientation (3 measurements per lens)
 - Overall stability of toric mark position
 - Overall lens fit acceptance (0-4 scale)
- The participant will be given a set of daily subjective questionnaires (Appendix 12) to be completed at home on days 1, 3 and 6 starting the morning after the dispensing visit (day 0), to reflect their lens wear experience at the time of rating. Participant will be given careful explanation of how and when to complete them. Questions will include:
 - Time of lens insertion and removal
 - Comfort after insertion (i.e. after lens settling), after 4, 8, and 12 hours, and just before lens removal (0-10 scale)
 - Dryness after 4, 8, and 12 hours, and just before lens removal (0-10 scale)
 - Visual quality/clarity after insertion (i.e. after lens settling), after 4, 8, and 12 hours, and just before lens removal (0-10 scale)
 - Vision stability after insertion (i.e. after lens settling), after 4, 8, and 12 hours, and just before lens removal (0-10 scale)

The participant will be asked to wear the study lenses for at least 12 hours per day and 6 days per week.

- Participant will be provided with sufficient contact lens supply.
- The participant will be discharged and reminded to return for the 1-week visit of lens pair #1 and to bring back all lens package foils.

4.8.4 1-WEEK FOLLOW-UP OF PAIR #1 & DISPENSING PAIR #2

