Participants will be asked to wear lenses for at least 4 hours prior to the visit appointment. Participants who attend without lenses in-situ (wearing lenses) for at least four hours will be rescheduled.

- The participant will be asked to score their subjective responses by reflecting on a typical day during the previous week of lens wear, as detailed in the subjective ratings form (Appendix 11) and includes the following:
 - Wear time at this visit (hours)
 - Wear time per day during previous 1 week (hours)
 - Comfortable wear time per day during previous 1 week (hours)
 - Overall comfort (0-10 scale)

- Overall dryness (0-10 scale)
 - Ease of insertion (0-10 scale)
 - Ease of removal (0-10 scale)
 - Overall visual quality/clarity (0-10 scale)
 - Overall visual stability (0-10 scale)
 - Overall satisfaction (0-10 scale)
 - Comments by participants
- Monocular and binocular logMAR visual acuity will be recorded with high contrast letters under high and low room illumination.
 - Lens surface and fit will then be assessed and graded according to the CVI grading scales for the following:
 - Lens wettability (0-4 scale)
 - Centration (mm)
 - Post-blink movement (mm)
 - Toric mark visibility
 - Lens orientation (3 measurements per lens)
 - Overall stability of toric mark position
 - Overall lens fit acceptance (0-4 scale)
 - The lenses will be removed and retained. The disposal procedures are detailed in Section 4.7.6.
 - Slit lamp biomicroscopy will be assessed according to the CVI approved study biomicroscopy CRF.
 - There will be a 10 minute wash-out before insertion of lens pair #2.
 - Lens pair #2 will be provided to participants in a manner which does not unmask the participant, as described in Section 4.7.4.
 - The lenses will be inserted by the participant.
 - Procedures of fit and assessment will be repeated as detailed in the dispensing visit, section 4.8.3.
 - The participant will be discharged and reminded to return for the 1-week visit of lens pair #2 and to bring back all lens package foils.

4.8.5 1-WEEK FOLLOW-UP OF PAIR #2 & DISPENSING PAIR #3

Participants will be asked to wear lenses for at least 4 hours prior to the visit appointment. Participants who attend without lenses in-situ (wearing lenses) for at least four hours will be rescheduled.

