 - Overall dryness (0-10 scale)
 - Ease of insertion (0-10 scale)
 - Ease of removal (0-10 scale)
 - Overall visual quality/clarity (0-10 scale)
 - Overall visual stability (0-10 scale)

- Overall satisfaction (0-10 scale)
- Comments by participants
- Participants will be asked their preference between lens pair #1, lens pair #2, and lens pair #3, for a number of considerations:
 - Overall comfort preference
 - Visual quality preference
 - Vision stability preference
 - Overall handling (lens insertion and removal) preference
 - Overall lens preference
- Monocular and binocular logMAR visual acuity will be recorded with high contrast letters under high and low room illumination.
- Lens surface and fit will then be assessed and graded according to the CVI grading scales for the following:
 - Lens wettability (0-4 scale)
 - Centration (mm)
 - Post-blink movement (mm)
 - Toric mark visibility
 - Lens orientation (3 measurements per lens)
 - Overall stability of toric mark position
 - Overall lens fit acceptance (0-4 scale)
- The lenses will be removed and retained. The disposal procedures are detailed in Section 4.7.6.
- Slit lamp biomicroscopy will be assessed according to the CVI approved study biomicroscopy CRF.
- Exit visual acuity will be performed.
- The study exit form will be completed when a participant exits the study. This will occur either at study completion, or if the participant is discontinued from the study at another time. A study exit form must be completed for all participants who have taken a study ID

number. If in the opinion of the investigator post-study follow-up visits are required, the exit form will be completed after the last follow-up visit.

- The participant will be discharged and will sign the study completion forms and receive remuneration for participating in the study.

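### Eye-level measures are tested separately in each eye and never combined, giving two correlated answers to one lens question and less precision; the primary ratings are not affected

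*Combined protocol and SAP*

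**What the plan says.** Section 11.2 sets the rule for all variables without restriction: "Analysis of variables will be conducted separately on each eye, and data will not be pooled". The same section sets significance at 0.05 without multiplicity adjustment. It names no study eye and gives no way to reconcile right-eye and left-eye results.

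The design in Section 4.1.1 is a "bilateral, randomized, cross-over dispensing study comparing the MD-T test lens against the 1-DAM-T and DACP-T control lenses". Section 4.8.3 assigns lenses by pair: the first pair "of contact lenses (either test or one of the control lenses) will be selected according to the randomization table". Lens type is therefore allocated to the participant for a period, and both eyes receive it.

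The outcomes fall into two groups.

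- **One value per participant.** The primary outcomes in Section 2 are comfort, dryness and visual quality, for example "Comfort and lens preference with respect to comfort (subjective ratings"). At dispensing, "The participant will be asked to give subjective binocular ratings for" comfort and vision (Section 4.8.3). The follow-up and home ratings are listed with no split by eye. Section 4.8.6 says: "Participants will be asked their preference between lens pair #1, lens pair #2, and lens pair #3". Binocular visual acuity is also a single value.
- **One value per eye.** Monocular visual acuity, wettability, centration, movement, orientation ("Lens orientation (3 measurements per lens"), fit acceptance and biomicroscopy (Sections 4.8.3 to 4.8.6).

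**The concern.** When both eyes wear the same lens, they are repeated measurements of one lens effect within a participant. The usual course is to combine them within the participant and report one estimate. Here each eye-level variable is tested twice. At one time point, comparing the test lens with two controls means four tests (2 eyes × 2 controls) where two would do.

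Two things are at stake. The first is interpretation. If the right eye shows a significant difference and the left does not, the plan does not say what is concluded, and the choice of which eye to stress would be made after seeing the data. The second is precision. Data already collected on the second eye are not used to sharpen the estimate.

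The eye-level measures are not among the primary outcomes listed in Section 2. They do bear on the general hypothesis of clinical performance in Section 3. Section 11.2 also introduces Table 5 as covering primary outcome variables, and that table includes visual acuity, lens parameters and biomicroscopy.

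**Working it through.** **1. The plan's own figure.** Section 11.1 gives a difference of 5, an SD of 12.6, two-sided alpha of 0.05, 80% power and N = 52. The standardised paired difference is 5/12.6 = 0.397. A paired t-test (noncentral t) needs n = 52, with power 80.2%; at alpha 0.10 it needs 41. Both match Table 4. This calculation concerns comfort scores, one per participant, so the eye rule does not enter it.

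**2. Variance.** Write an eye-level outcome as lens + period + eye + participant + participant-by-period (variance a) + participant-by-eye + residual (variance b).

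- Within one eye, the difference between two lenses has variance 2(a + b). The participant and participant-by-eye terms cancel.
- The covariance of that difference between the two eyes is 2a, so the between-eye correlation is ρ = a/(a + b).
- The two-eye mean difference has variance 2(a + b/2) = 2(a + b) × (1 + ρ)/2.

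Averaging therefore multiplies the single-eye variance by (1 + ρ)/2. The documents do not give ρ, so a range is assumed.

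**3. Power and disagreement.** No effect size or SD is given for any eye-level outcome. As an illustration, suppose each eye alone has the standardised effect of step 1. The expected z is then 0.397 × √52 = 2.86, and power by the normal approximation is about 82%. For the two-eye mean, the expected z is 2.86/√((1 + ρ)/2). Disagreement means exactly one eye is significant. It comes from a bivariate normal with both means 2.86 and correlation ρ.

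| ρ (assumed) | Variance ratio | Variance saved | Power, two-eye mean | Eyes disagree |
|---|---|---|---|---|
| 0.3 | 0.65 | 35% | 94% | 25.2% |
| 0.5 | 0.75 | 25% | 91% | 21.3% |
| 0.7 | 0.85 | 15% | 87% | 16.5% |
| 0.9 | 0.95 | 5% | 84% | 9.5% |

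At ρ = 0.9 the standard error falls by only about 3%, since √0.95 = 0.975. At ρ = 1 the gain is zero.

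**4. No true difference.** The chance that at least one of the two eyes is significant at 0.05 is 9.5%, 9.1%, 8.4% and 7.0% for ρ = 0.3, 0.5, 0.7 and 0.9. This describes the pair of tests; the plan does not use it as a decision rule.

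**5. Which mixed model.** A model with participant and participant-by-period random effects, but without participant-by-eye, puts stable differences between a person's eyes into the residual. This was simulated with 52 participants, 3 periods and 2 eyes, scaling the single-eye variance, excluding stable eye effects, to 1.

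- With ρ = 0.3 and stable eye variance 1.5, the participant-by-period component is estimated as zero in 99% of trials. The model's variance for the lens effect is then 0.91 instead of 0.65.
- With ρ = 0.5 and stable eye variance 2, it is 1.04 instead of 0.75, no better than one eye.

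The participant-by-eye term is needed, or else the simple two-eye mean.

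**The case against.** The case for leaving the plan alone has real substance.

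- **The primary analysis is untouched.** A reader might infer from the unrestricted wording that the primary ratings are split by eye or that N = 52 is wrong. The documents do not support this: the dispensing ratings are binocular, preferences are between pairs, and the sample size rests on comfort scores.
- **Error control.** A reader might infer a false-positive rate of 7% to 9.5%. The plan nowhere says that a result in either eye is enough. Each eye's test holds its own 5% level, and the absence of multiplicity adjustment is stated openly for all outcomes.
- **Validity.** Separate analysis is inefficient but not wrong, and it avoids the worse mistake of counting two eyes as independent participants. Reporting by eye also has a rationale: lens power is optimised for each eye (Section 4.8.2), and adverse events are recorded by eye (Section 7.3).
- **Size.** The correlation is assumed, the 82% power is borrowed from a comfort calculation, and the gain is small if the eyes agree closely.
- **Status.** Text after the primary outcomes in Section 2 is redacted, so the formal standing of the eye-level measures cannot be read, and no visible success criterion rests on them.

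All of this stands and limits the point to eye-level measures and to a modest size. None of it supplies the missing rule for discordant eyes or a reason to forgo the second eye's information.

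**Conclusion.** The point holds for eye-level measures only. For these, Section 11.2 produces two correlated, unadjusted tests of one participant-level contrast, leaves a discordant result without an interpretation, and gives up some precision. Over an assumed ρ of 0.3 to 0.9 the variance forgone is 35% to 5%. Disagreement in about 25% to 10% of trials rests on the further assumption that each eye alone has about 82% power. It would be wrong to conclude that the planned tests are invalid or that the primary comparison is weakened. This is an inexpensive improvement to the measures outside the primary list in Section 2.

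**What to change.** Replace the sentence in Section 11.2 with:

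> Eye-level continuous outcomes will be analysed once per lens comparison, using the participant's mean of the two eyes in each period (signed horizontal centration and orientation first converted to a nasal/temporal convention), or equivalently a mixed model with lens, period and eye as fixed effects and participant, participant-by-period and participant-by-eye as random effects. Ordinal grades will be analysed once per lens comparison with an ordinal model clustered on participant. Eyes will not be treated as independent participants, and single-eye summaries will be descriptive.

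The nasal/temporal step matters because a mirror-symmetric shift would cancel if raw left and right signs were averaged. An analysis of the worse eye is not offered for ordinal grades, because it changes what is estimated.

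The cost is a change of wording and slightly more analysis work, with no new data and no change to N. The two-eye means can go into the repeated-measures or paired tests already in Table 5. Recording of adverse events by eye is unaffected. The downside is that a lens effect confined to one eye would be seen only in the descriptive summaries.

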3 HYPOTHESIS

The study hypothesis is that the MyDay toric test lens (MD-T) will perform as well or better clinically than the two control lenses: 1-Day Acuvue Moist for Astigmatism (1-DAM-T) and Dailies AquaComfort Plus Toric (DACP-T).

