11 STATISTICAL ANALYSIS AND DATA MANAGEMENT

11.1 SAMPLE SIZE CALCULATION

The maximum sample size will be 52. For a two-sided paired t-test with an alpha of 0.05 and a power goal of 80%, this will allow an effect size as small as 0.28 to be detected. This sample size will give approximately 80% confidence to detect a difference of 5 points in comfort ratings.

Table 4 shows the sample size determination for a difference between two means in comfort scores. Sample sizes with 80% power are shown at two different alpha levels (alpha = 0.05 and alpha = 0.10). Assuming a standard deviation of 12.6 points, a sample size of 52 participants provides 80% power to detect a trend in difference of comfort scores between 5 points on a 100-point scale.

Table 4: Sample size calculation

Mean individual	Mean individual	Sample size	Sample size
-----------------	-----------------	-------------	-------------

difference in score	standard deviation	(p = 0.05)	(p = 0.10)
5	12.6	52	41
7	17.6	52	41

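### Section 11.2 lists Tukey HSD post hocs yet rules out multiplicity adjustment, and the sample size rests on the unadjusted paired t-test

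*Combined protocol and SAP*

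**What the plan says.** Section 4.1.1 describes a three-lens crossover "comparing the MD-T test lens against the 1-DAM-T and DACP-T control lenses". Three lenses give three pairs, two of which are test against control.

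Section 11.2, Table 5, covers numeric scales and other continuous variables in one row. For the effect of lens type, that row's test cell holds RMANOVA/MANOVA, Friedman, Wilcoxon, "Tukey HSD post hocs", paired t-test and chi-square. The table presents these as anticipated procedures and gives no rule for choosing among them. The sentence after the table sets the threshold at 0.05 "with no adjustments for multiple comparisons" and does not limit that statement to any kind of comparison.

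Section 11.1 bases the sample size on one test: "For a two-sided paired t-test with an alpha of 0.05 and a power goal of 80" percent. It adds: "Assuming a standard deviation of 12.6 points, a sample size of 52 participants provides 80% power", for a "difference of comfort scores between 5 points on a 100-point scale".

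Section 3 states the hypothesis that MD-T "will perform as well or better clinically than the two control lenses".

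**The concern.** Tukey HSD controls the error rate over all pairwise comparisons among the lenses, so it requires a larger test statistic for each pair than an unadjusted test does. An analyst who uses it departs from the no-adjustment sentence, and one who follows that sentence cannot use it. Both routes are on the page for the same variables, and nothing says which one settles the comparison of MD-T with each control.

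Two things are at stake. A result of moderate size can be called significant or not according to the listed test used, and that choice can be made after the data are seen. And if Tukey is used, the power is not the power for which the trial was sized.

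**Working it through.** **Inputs.** From Section 11.1: difference 5, SD of individual differences 12.6, two-sided alpha 0.05, N = 52. From Section 4.6.1: 52 dispensed, 45 target completers. From Section 4.1.1: three lenses. Assumed here: the SD of 12.6 holds for every pair of lenses, and data are complete.

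**1. Reproduce the plan's figure.** Paired t-test power comes from the noncentral t distribution with df = n − 1 and noncentrality (5/12.6)·√n.
- n = 52: noncentrality 0.397 × 7.211 = 2.86, critical value 2.008, power 80.2%.
- 52 is the smallest n that reaches 80%. At alpha 0.10 the smallest is 41. The 7/17.6 row also gives 52 and 41. Table 4 is therefore the unadjusted paired t-test with 12.6 as the SD of differences.
- n = 45: noncentrality 0.397 × 6.708 = 2.66, critical value 2.015, power 74.0%.

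Section 11.1 also says "this will allow an effect size as small as 0.28 to be detected". That does not match 5/12.6 = 0.397; it equals 5/(12.6·√2). This is a separate matter, and the figures here use 5 and 12.6 directly.

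**2. The same contrast under Tukey.** The critical value is |t| = q(0.95; 3, df)/√2, with df = 2(n − 1) from a one-way repeated-measures ANOVA.

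| | n = 52 | n = 45 |
|---|---|---|
| Error df | 102 | 88 |
| q | 3.364 | 3.371 |
| Tukey critical value | 2.378 | 2.384 |
| Equivalent per-pair two-sided p | 0.019 | 0.019 |
| Power, Tukey | 68.5% | 61.0% |
| Power, paired t-test | 80.2% | 74.0% |

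With the more cautious df = n − 1, Tukey power is 67.3% and 59.6%. About 66 completers would be needed for 80% under Tukey (68 with df = n − 1).

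**3. Size of the disputed band.** The smallest significant mean difference is the critical value × 12.6/√n. At n = 52, 12.6/√52 = 1.747.
- Paired t-test: 2.008 × 1.747 = 3.51 points.
- Tukey: 2.378 × 1.747 = 4.16 points.

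At the assumed SD, observed differences between about 3.5 and 4.2 points get opposite answers.

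**4. How often the verdict changes.** In 40,000 simulated trials at n = 52 with a true difference of 5, 11.5% were significant by the paired t-test and not by Tukey, and essentially none the reverse. Of results with unadjusted p between 0.019 and 0.05, about 76% changed verdict. The share is below 100% because Tukey uses the pooled error term while the paired t-test uses the SD of that pair alone.

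**5. What the unadjusted route costs.** With no true differences, the simulated chance of at least one false positive per outcome is about 9% over the two test-versus-control contrasts and about 12% over all three pairs. If MD-T truly differs by 5 points from both controls, the simulated chance that both paired t-tests are significant is about 69% at n = 52 and 60% at n = 45.

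**The case against.** The best defence is that the two statements address different things: no adjustment across the many outcomes, with Tukey used only as the follow-up to an RMANOVA within one outcome. That reading is coherent, but the document does not state it. If it was intended, Tukey becomes the deciding comparison within each outcome, and Section 11.1 has sized the trial on a different test.

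A second defence is that Table 5 only anticipates procedures for several kinds of variable and includes the paired t-test. That stands as far as it goes: the plan does not prescribe Tukey, and a reader who inferred that the trial as designed has only 69% power would go too far. The sizing test is available; it is just not named as decisive.

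Third, Section 4.1.2 keeps investigators masked until the database is locked. This does not fix the deciding test before the results are analysed.

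Two stronger readings should be resisted. One is that every result with unadjusted p between 0.019 and 0.05 flips; about three quarters do, even with equal variances. The other is that Section 3 already requires significance against both controls. It names two controls and speaks of performing as well or better, but gives neither a significance rule nor a margin. Two significant difference tests would show a difference from each control, which is another claim. That rule also has joint power of only about 69% and 60%, so it does not restore the planned 80% either.

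Finally, dropping control versus control is a choice. A three-lens RMANOVA may properly examine all pairs, and keeping Tukey with a larger sample would also be consistent.

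**Conclusion.** The contradiction in Section 11.2 is real and should be corrected. As written, the section offers an adjusted and an unadjusted comparison for the same effect, declares that nothing is adjusted, and names neither as decisive. Choosing Tukey costs about 12 percentage points of power per contrast at 52 participants (80.2% to 68.5%) and 13 at 45 (74.0% to 61.0%), and changes the verdict in roughly one trial in nine at 52.

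These figures rest on the plan's 5 points and 12.6, the same SD for every lens pair, and complete data. The choice of error degrees of freedom moves Tukey power by less than 1.5 points. Unequal variances would loosen the correspondence between the two tests but would not remove the contradiction. The finding concerns comparisons between lenses within one outcome; it does not address multiplicity across the three primary outcomes or the missing margin for the Section 3 hypothesis.

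**What to change.** In Section 11.2:
- Delete the Tukey entry from Table 5.
- For the numeric ratings, name the paired t-tests of MD-T vs 1-DAM-T and MD-T vs DACP-T, each at two-sided 0.05, as the deciding comparisons. Report control versus control descriptively.

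In Section 11.1:
- State that the 80% applies to each contrast separately at n = 52, and is 74% at the 45 target completers.
- If a claim of a difference from both controls is intended, say so. No adjustment between the two contrasts is then needed, but state the joint power of about 69% at 52 and 60% at 45.

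Do not present two significant difference tests as the test of the Section 3 hypothesis.

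The cost is one table entry and a few sentences, with no added participants. The statistical price is that, if each contrast is claimed on its own, the chance of at least one false positive over the two is about 9% per outcome. The plan's no-adjustment rule already accepts this. The alternative is to keep Tukey, remove the no-adjustment sentence for lens comparisons, and re-size to about 66 completers.

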4.6 STUDY POPULATION

4.6.1 NUMBER OF PARTICIPANTS

Up to 52 participants will be dispensed / randomized with study products, with a target of 45 completing the study. Participants will be recruited using CCLR records and advertising approved by the UW Office of Research Ethics (Appendices 2, 3a, and 3b). Each participant will be given a unique ID number. Additionally, all participants must meet the study inclusion and none of the exclusion criteria listed below.

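### Section 11.2 excludes only single missing values, but the three-lens tests in Table 5 drop a participant's whole set, so the rule cannot be carried out with them

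*Combined protocol and SAP*

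**What the plan says.** Section 11.2 sets the analysis set in one sentence: "All participants who were evaluated will be used in the analysis". The next sentence gives the missing-data rule: "In the event of missing data, individual data points will be excluded in the analysis and not extrapolated from the collected data". For the effect of lens type on rating scales and visual acuity, Table 5 offers "RMANOVA/MANOVA/ Friedman /Wilcoxon matched pairs test", followed by Tukey HSD post hocs, the paired t-test and the chi-square test. The table calls these procedures anticipated. It does not say which applies to which variable, how day and hour enter the analysis of home ratings, or what happens to a participant with an incomplete set. On software, the section says: "Data analysis will be conducted using Statistica and / or SPSS".

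Section 4.6.1 allows up to 52 participants to be randomised, "with a target of 45 completing the study". Under section 4.8.3 each lens comes with questionnaires "to be completed at home on days 1, 3 and 6". Comfort and visual quality are rated at five times on each of those days, and dryness at four. The follow-up visits (sections 4.8.4 to 4.8.6) add one overall rating of comfort, dryness and visual quality per lens.

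**The concern.** Ordinary repeated-measures ANOVA, MANOVA and Friedman need a full row of values from each participant. One missing lens, day or hour removes all the other values that person gave to that model. That is deletion of participants, whereas section 11.2 promises deletion of data points. An analyst holding both statements has to break one of them, and the plan does not say which.

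Two things are at stake. The first is precision: ratings that were collected go unused. The second is validity: an analysis of complete participants is safe only if they resemble a random subset of everyone evaluated. Because the test and model structure are left open, the number analysed is also undefined until someone chooses, possibly after seeing the data.

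**Working it through.** **1. Reproduce the plan's sample size.** Inputs from section 11.1 and Table 4: paired t-test, two-sided alpha 0.05, 80% power, difference 5, SD 12.6. The standardised effect is 5/12.6 = 0.397. Power comes from the noncentral t distribution with n − 1 degrees of freedom and noncentrality 0.397 × √n. The smallest n reaching 80% is 52 (power 80.2%), and 41 at alpha 0.10. Both match Table 4. Section 11.1 also quotes an effect size of 0.28. That equals 5/(12.6 × √2) and does not fit the paired calculation, so the Table 4 inputs are used here.

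**2. Loss that needs no assumed missing rate.** 52 randomised − 45 target completers = 7, and 7/52 = 13.5%. Anyone among these 7 evaluated on one or two lenses counts as evaluated under section 11.2, yet cannot enter a three-lens complete-set test. At n = 45 the noncentrality is 0.397 × √45 = 2.66 and power is 74.0%, against 80.2% at n = 52.

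**3. Home ratings.** The number of values one model needs per participant, k, follows from section 4.8.3:

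- one day and one hour, three lenses: k = 3
- one hour over three days, three lenses: 3 × 3 = 9
- comfort without the 8- and 12-hour ratings: 3 lenses × 3 days × 3 times = 27
- all dryness ratings: 3 × 3 × 4 = 36
- all comfort ratings: 3 × 3 × 5 = 45

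The documents give no missing rate. Assume each rating is missing independently with probability m. The share of complete participants is then (1 − m)^k. The bracketed counts are out of 52.

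| k | m = 1% | m = 2% | m = 5% |
|---|---|---|---|
| 3 | 97% (50) | 94% (49) | 86% (45) |
| 9 | 91% (48) | 83% (43) | 63% (33) |
| 27 | 76% (40) | 58% (30) | 25% (13) |
| 36 | 70% (36) | 48% (25) | 16% (8) |
| 45 | 64% (33) | 40% (21) | 10% (5) |

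A two-lens paired test at one day and hour has k = 2. At m = 2% it keeps 0.98² = 96%, about 50 of 52.

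**4. Look for a passage that resolves it.** None does. Section 4.8 says that data from visits outside the window will be assessed for inclusion in the analysis population, which is a further departure from using everyone. Section 12.6 has the investigator review the take-home questionnaires with the participant. That may reduce gaps, but it does not say how remaining gaps are analysed.

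**The case against.** The strongest reply is that Table 5 is a menu. The paired t-test and Wilcoxon are on it, section 11.1 is built on a paired t-test, and those tests come close to the missing-data rule because a gap removes a person only from one comparison. The sentence on the analysis set could also be read as defining who is eligible, with n varying by test. This stands as a limit: the conflict is with the three-lens tests and not with every listed test. It does not remove the conflict, because those tests are listed first and no rule selects among the options.

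A reader might infer that the home-rating analyses will lose much of the sample. The documents do not support that. They specify no model of lens by day by time, and the missing rates above are assumptions. At one day and hour the loss is small. Gaps clustered within a few participants would also reduce it.

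A reader might also infer that the home ratings carry the primary variables. Section 2 names comfort, dryness and visual quality ratings without saying whether the diary or the visit form is meant. The overall visit ratings fit at least as well, and there the main foreseeable loss is the 7 planned non-completers.

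Nor can it be shown that pooled-error post hocs give intervals that are too narrow for the MD-T contrasts. That needs a separate SD for each lens difference, and the plan gives none.

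**Conclusion.** The concern holds in a limited form. The missing-data rule in section 11.2 cannot be carried out with RMANOVA, MANOVA or Friedman as ordinarily run, and nothing else in the document settles which statement gives way.

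The size that rests on the plan's own figures is up to 7 of 52 participants lost from every three-lens test. This assumes the maximum is randomised, the completion target is just met, and all seven were evaluated on at least one lens. The matching fall in power from 80% to 74% is a paired-test yardstick and not the power of an RMANOVA. A mixed model recovers only part of it, since someone who wore a single lens adds almost nothing to a within-person lens contrast.

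For the home ratings the size is conditional. At an assumed 2% of ratings missing independently, complete participants range from 94% down to 40%, depending on a model structure the plan does not state.

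**What to change.** In Table 5, make a linear mixed model the main analysis of lens effect for ratings and visual acuity. SPSS, already named, can fit it with its MIXED procedure.

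- **Fixed effects:** lens and period, because this is a three-period crossover; add day and hour for the home ratings.
- **One value per lens** (week-1 ratings, visual acuity at a given visit and lighting level): unstructured covariance across the three lenses, with no separate participant intercept, which would be redundant.
- **Home ratings:** participant and participant-by-lens random effects, with lens-specific variances where they can be estimated.
- **Inference:** Satterthwaite or Kenward-Roger degrees of freedom. Report MD-T minus each control with a 95% confidence interval, using all available ratings.
- **Sensitivity analysis:** Wilcoxon on available pairs.

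This makes the rule of excluding only individual data points workable. The model is valid if values are missing at random given the observed ratings. It does not by itself deal with a 12-hour rating that is absent because discomfort shortened wear, a possibility section 7.2 acknowledges.

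The cost is SAP wording and slightly more analysis work. No new data, visits or participants are needed.
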